6.1.4. Prior and Concomitant Medications

Summaries will be provided for the asthma medications before study treatment, as well as summaries for both asthma and non-asthma medication during the treatment period and during follow-up period. A total column will be included for the all summaries. Listings will be provided for the asthma and non-asthma concomitant medications.

Non-Asthma medication tables will report by Anatomical Therapeutic Chemical (ATC) level 1 and ingredient. Asthma medication tables will report by respiratory medication class (RMC) and ingredient.

Multi-ingredient medications will be presented according to their combination ATC classification rather than the classification of the ingredients.

6.1.5. Treatment Compliance

Treatment compliance will be assessed during the treatment period by dose group and total.

For the treatment period, the actual total number of doses received by each subject will be calculated as the sum of (dose counter start value – dose counter stop value) over all inhalers dispensed to the subject during the treatment period and returned prior to or at the EOT/EW visit, and percentage compliance will be calculated as follows:

$$\text{Treatment Compliance} = \frac{\text{total number of doses received}}{\text{treatment stop date} - \text{treatment start date} + 1} \times 100.$$

In interim analysis, treatment compliance will be calculated based on data until the day before visit 5 (i.e., treatment stop date will be replaced with the day before visit 5). Details on the derivations are provided in Section 11.6.2.

7. EFFICACY ANALYSES

This is an open-label study and the efficacy will be assessed in an exploratory manner. Therefore, no efficacy endpoint is defined and the efficacy will be assessed as other endpoints.

8. SAFETY ANALYSES

The safety analyses will be based on the ITT population, unless otherwise specified. All outputs unless specified otherwise will be produced for the interim analysis and final analysis.

8.1. Extent of Exposure

Overall extent of exposure to study treatment will be summarized in increments of 4 weeks for ≥ 1 day, ≥ 4 weeks, ≥ 8 weeks, ≥ 12 weeks, ≥ 16 weeks, ≥ 20 weeks, ≥ 24 weeks, ≥ 28 weeks, ≥ 32 weeks, ≥ 36 weeks, ≥ 40 weeks, ≥ 44 weeks, ≥ 48 weeks, ≥ 52 weeks, in addition to providing summary statistics and total treatment exposure (person-year).

8.2. Adverse Events Analyses

Adverse events analyses including the analysis of adverse events (AEs), Serious (SAEs) and other significant AEs will be based on GSK Core Data Standards. The details of the planned displays are provided in [Appendix 11: List of Data Displays](#).

All AEs will be classified using the standard GSK Medical Dictionary for Regulatory Activities (MedDRA) dictionary, and grouped by SOC and PT, unless otherwise stated. The investigator will evaluate all AEs with respect to seriousness, severity, and causality.

The tabular summary for each type of AE listed below will include the number of participants who reported at least one event, and percentage of participants who reported at least one AE (incidence) for each SOC (where applicable), each PT, and overall. By default, adverse events will be sorted by MedDRA SOCs, in descending order from the SOC with the highest total incidence (i.e., summed across all dose groups) for any adverse event within the class, to the SOC with the lowest total incidence. If the total incidence for any two or more adverse events is equal, the events will be presented in alphabetical order. Only SOCs with observed AE PTs will be presented. Repeat sort order for MedDRA PTs within each SOC.

In principle, all safety analyses will be provided by dose group and total. However, due to Japan regulatory authority requirement, AE analyses by dose at the time of onset of the AE will be prepared in final analyses of this study. Note that dose at the time of onset of the AE will be decided by allocated dose even if a given subject has incorrect study treatment in certain period (but not during all period). If a given subject has incorrect study treatment during all period, then this subject will be analysed according to the treatment which he/she received. In interim analyses, selected tables will be provided. Please refer to Section [11.11.5](#).

Each type of the following will be summarized for both approaches (i.e., by dose group and total, by dose at the time of onset of the AE)

- AE overview during treatment period
- All AEs during treatment period (by SOC and PT; by SOC and PT and maximum severity)
- Drug related AEs during treatment period (by SOC and PT; by SOC and PT and maximum severity)
- Serious AEs during treatment period (by SOC and PT)
- AEs resulting in withdrawal from study (by SOC and PT)

- AEs of Special Interest during treatment period (by SOC and PT)
- Most Common Adverse Events during treatment period (3% or More of subjects in Any Treatment Group) (by PT)

The following AE summaries will be provided only by dose group and total.

- All AEs adjusted for exposure (per thousand person years) during treatment period (by SOC and PT)
- All AEs during follow-up period (by SOC and PT)
- Drug related AEs adjusted for exposure (per thousand person years) during treatment period (by SOC and PT)
- Drug related AEs during treatment period and follow-up period (by SOC and PT)
- All AEs for week 0-12, week 13-24, week 25-36 and week 37-52 during treatment period (by SOC and PT)
- All AEs for week 0-24, week 25-52 during treatment period (by SOC and PT)
- Serious AEs adjusted for exposure (per thousand person years) during treatment period (by SOC and PT)
- AEs of Special Interest adjusted for exposure (per thousand person years) during treatment period (by SOC and PT)
- Common Non-Serious AEs by SOC and PT during treatment period (Number of Subjects and Occurrences) (5% or More of subjects in Any Treatment Group)
- Summary of Serious Adverse Events by System Organ Class and Preferred Term during treatment period (Number of Participants and Occurrences)
- Major Adverse Cardiac Events
- Serious Drug Related Adverse Events during treatment period (for PLS, final analysis only)
- Non-Serious Drug Related Adverse Events during treatment period (for PLS, final analysis only)

The following AE listings will be provided. These listing include information of dose group, not dose at AE.

- All AEs, Fatal serious AEs, Non-Fatal AEs, AEs leading to permanent discontinuation of study treatment or withdrawal from study
- Relationship of AE SOCs, PTs and Verbatim text
- Reasons for considering as a serious AE

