#### 10.3.2. Safety Analyses

All safety analyses will be performed on the ITT Population.

Endpoint	Statistical Analysis Methods
Primary	
The primary endpoint is incidence and type of AEs/SAEs. This endpoint will be summarized using the following two approaches:
 
 
1. Summary statistics will be provided for the integration of the groups and for each group separately (only FF/UMEC/VI 100/62.5/25 mcg, only FF/UMEC/VI 200/62.5/25 mcg and switching medication from FF/UMEC/VI 100/62.5/25 mcg to FF/UMEC/VI 200/62.5/25 mcg).
 
2. Summary statistics will be provided by the dose received at the time of experiencing the AE. (FF/UMEC/VI 100/62.5/25 mcg and FF/UMEC/VI 200/62.5/25 mcg)
 
 
The number and proportion of subjects experiencing at least one AE will be calculated and presented by system organ class (SOC) and by preferred term (PT). Summary statistics will also be presented for all AEs, treatment-related AEs, SAEs, AEs leading to treatment or study discontinuation, and AESI.

Secondary	
Secondary endpoints will be summarized using the approach described in approach 1 above (i.e., provided for only FF/UMEC/VI 100/62.5/25 mcg, only FF/UMEC/VI 200/62.5/25 mcg and switching medication from FF/UMEC/VI 100/62.5/25 mcg to FF/UMEC/VI 200/62.5/25 mcg).
 
Specific details will be provided in the Reporting and Analysis Plan (RAP).

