2. SUMMARY OF KEY PROTOCOL INFORMATION

2.1. Changes to the Protocol Defined Statistical Analysis Plan

There were no changes or deviations to the originally planned statistical analysis specified in the protocol (Dated: 13/MAR/2017), amendment 1 (Dated:24/MAY/2017) or amendment 2 (Dated: 25/OCT/2017).

In order to comply with regulatory guidance where the protocol referred to “Subjects” the analysis plan refers to “Participants”, with the exception of displays and study populations.

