4.1. Protocol Deviations

Important protocol deviations (including deviations related to study inclusion/exclusion criteria, conduct of the trial, patient management or patient assessment) will be summarised and listed.

Protocol deviations will be tracked by the study team throughout the conduct of the study in accordance with the Protocol Deviation Management Plan [1Aug2018 Version 3.0].

- Data will be reviewed prior to freezing the database to ensure all important deviations are captured and categorised on the protocol deviations dataset.
- Participants who received an incorrect treatment will be captured as an important protocol deviation. The incorrect treatment will be identified in eCRF (if “No” to the question “Did the subject receive the correct treatment?” then this participants will be regarded as having received an incorrect container).
- This dataset will be the basis for the summaries and listings of protocol deviations.

A separate listing of all inclusion/exclusion criteria deviations will also be provided. This will be based on data as recorded on the inclusion/exclusion page of the eCRF.

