11.3.2.2. In Final Analyses

For treatment group of “only FF/UMEC/VI 100/62.5/25” and “only FF/UMEC/VI 200/62.5/25”, the table below will be applied (see Section 11.5.1 for treatment group description).

Analysis Window		Analysis Timepoint
Beginning Timepoint	Ending Timepoint	
Day 1	Day 84	Week 0-12
Day 85	Day 168	Week 13-24
Day 169	Day 252	Week 25-36
Day 253	Day 365 Or The day of visit 7 (week 52 visit) if this is later than Day 365	Week 37-52
Day 1	Day 168	Week 0-24
Day 169	Day 365 Or The day of visit 7 (week 52 visit) if this is later than Day 365	Week 25-52

For treatment group of “FF/UMEC/VI 100/62.5/25 to FF/UMEC/VI 200/62.5/25”, the table below will be applied (see Section 5.1 for treatment group description). The reason to use separate analysis window for “FF/UMEC/VI 100/62.5/25 to FF/UMEC/VI 200/62.5/25” is to consider the day of switched treatment (i.e. the day of week 24).

Analysis Window		Analysis Timepoint
Beginning Timepoint	Ending Timepoint	
Day 1	Day 84	Week 0-12
Day 85	The day before visit 5 (week 24 visit)	Week 13-24
The day of visit 5 (week 24 visit)	Day 252	Week 25-36
Day 253	Day 365 Or The day of visit 7 (week 52 visit) if this is later than Day 365	Week 37-52
Day 1	The day before visit 5 (week 24 visit)	Week 0-24
The day of visit 5 (week 24 visit)	Day 365 Or The day of visit 7 (week 52 visit) if this is later than Day 365	Week 25-52

11.3.2.3. By dose at the time of onset of the AEs (by dose at AE)

For treatment group of “only FF/UMEC/VI 100/62.5/25” and “only FF/UMEC/VI 200/62.5/25”, the approach “by dose at AE” will summarize AEs during treatment period as each dose.

For treatment group of “FF/UMEC/VI 100/62.5/25 to FF/UMEC/VI 200/62.5/25”, the table below will be applied for an approach “by dose at AE” analyses.

Analysis Window		By dose at AE
Beginning Timepoint	Ending Timepoint	
Day 1	The day before visit 5 (week 24 visit)	As FF/UMEC/VI 100/62.5/25
The day of visit 5 (week 24 visit)	Day 365 Or The day of visit 7 (week 52 visit) if this is later than Day 365	As FF/UMEC/VI 200/62.5/25

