11.6. Appendix 6: Derived and Transformed Data

11.6.1. General

Multiple Measurements at One Analysis Time Point

• If there are two values within a time window, the value closest to the target day for that window will be used. If values are the same distance from the target, then the mean will be taken.• Participants having both High and Low values for Normal Ranges at any post-baseline visit for safety parameters will be counted in both the High and Low categories of “Any visit post-baseline” row of related summary tables. This will also be applicable to relevant Potential Clinical Importance summary tables.
Study Day

• Calculated as the number of days from First Dose Date:
• Ref Date = Missing → Study Day = Missing• Ref Date < Treatment Start Date → Study Day = Ref Date – Treatment Start Date• Ref Date ≥ Treatment Start Date → Study Day = Ref Date – (Treatment Start Date) + 1

Example of Handling the Incorrect Treatment and Dose at the Timing of Onset of the AE								
--	--	--	--	--	--	--	--	--

Here are the examples 1- 3 which a given subject had the incorrect treatment in certain period or all periods in treatment period (week 0 to week 52). It is assumed that all participants here complete study (i.e., do not withdraw).

Example	1			2			3		
Dose group	FF/UMEC/VI 100/62.5/25			FF/UMEC/VI 100/62.5/25 to FF/UMEC/VI 200/62.5/25			FF/UMEC/VI 100/62.5/25		
allocated dose at week0	FF/UMEC/VI 100/62.5/25			FF/UMEC/VI 100/62.5/25			FF/UMEC/VI 200/62.5/25		
Switch treatment at week24	No			Yes			No		
Plan dose/ Actual dose/ dose at AE	Plan	Actual	dose at AE	Plan	Actual	dose at AE	Plan	Actual	dose at AE
week0 -4	FF100	FF100	FF100	FF100	FF100	FF100	FF200	FF100	FF100
week4 - 12	FF100	FF100	FF100	FF100	FF200	FF100	FF200	FF100	FF100
week12 - 24	FF100	FF100	FF100	FF100	FF100	FF100	FF200	FF100	FF100
week24 - 36	FF100	FF100	FF100	FF200	FF200	FF200	FF200	FF100	FF100
week36 - 52	FF100	FF200	FF100	FF200	FF100	FF200	FF200	FF100	FF100

Example 1 is the case that a given participant was allocated FF/UMEC/VI 100/62.5/25 at week0 and not switch the study treatment at week24, but had incorrect treatment (i.e., FF/UMEC/VI 200/62.5/25) at week 36 to 52. Therefore, as described in Section 5.1 and Section 8.2, dose group for this participant will be FF/UMEC/VI 100/62.5/25, and AE at week 36 – 52 will be handled as AE at FF/UMEC/VI 100/62.5/25 for dose at AE analyses.

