Example 2 is the case that a given participant was allocated FF/UMEC/VI 100/62.5/25 at week0 and switched the study treatment at week24, but had incorrect treatment (i.e., FF/UMEC/VI 200/62.5/25 at week 4-12 and FF/UMEC/VI 100/62.5/25 at week 36-52) at two periods. Therefore, as described in Section 5.1 and Section 8.2, dose group for this participant will be FF/UMEC/VI 100/62.5/25 to FF/UMEC/VI 200/62.5/25, and AE at week 4 – 12 will be handled as AE at FF/UMEC/VI 100/62.5/25 and AE at week 36 – 52 will be handled as AE at FF/UMEC/VI 200/62.5/25 for dose at AE analyses.

Example 3 is the case that a given participant was allocated FF/UMEC/VI 200/62.5/25 at week0 and not switch the study treatment at week24, but had incorrect treatment (i.e., FF/UMEC/VI 100/62.5/25) during all periods. This participant HAD incorrect treatment during all periods. Therefore, as described in Section 5.1 and Section 8.2, dose group for this participant will be FF/UMEC/VI 100/62.5/25, and AE at any time will be handled as AE at FF/UMEC/VI 100/62.5/25 for dose at AE analyses.

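### The final dose-at-AE tables use allocated dose for part-period strength errors, where the protocol specifies dose received, and the SAP declares no change

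*SAP*

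**What the plan says.** Protocol 10.3.2 summarises the primary endpoint in two ways. The first is by dose group. The second is worded: "Summary statistics will be provided by the dose received at the time of experiencing the AE". The ITT definitions in Protocol 10.2 and SAP section 4 are also as-treated.

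SAP 8.2 gives a different rule for the second approach. Where the wrong strength was received in part of the period, the dose at onset "will be decided by allocated dose even if a given subject has incorrect study treatment in certain period (but not during all period". Only when every visit records incorrect treatment does the SAP use the treatment received (SAP 5.1.2.2 and 8.2).

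SAP 11.6.1 illustrates the rule. In Example 1 the actual strength in weeks 36–52 was 200, yet an AE in that interval "will be handled as AE at FF/UMEC/VI 100/62.5/25 for dose at AE analyses". In Example 2 the participant switched as planned at Week 24 "but had incorrect treatment (i.e., FF/UMEC/VI 200/62.5/25 at week 4-12 and FF/UMEC/VI 100/62.5/25 at week 36-52) at two periods", and AEs in both intervals again follow the plan. For participants who do not switch, SAP 11.3.2.3 says only that the approach "will summarize AEs during treatment period as each dose".

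SAP 2.1 states: "There were no changes or deviations to the originally planned statistical analysis specified in the protocol".

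**The concern.** The SAP replaces received dose with allocated dose in a protocol-defined summary of the primary endpoint and does not record the change. It is also inconsistent with itself. Received dose is used when all intervals are wrong, but a single correct interval returns the whole record to allocated dose. On the SAP's own intervals, a participant correctly supplied only in weeks 0–4 would have 48 of 52 weeks booked to a strength not taken.

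These are the only planned AE summaries by dose at onset. SAP 5.1.2.2 and 8.2 say they exist because the Japanese authority requires them. Fourteen final tables carry dose at AE in their titles (12.4–12.5, 12.9–12.10, 12.12–12.13, 12.16–12.17, 12.24–12.25, 12.28–12.29, 12.31–12.32), and they include SAEs, AEs leading to withdrawal and AESIs. Strength-specific counts have a stated purpose: Protocol 5.4 rules out step-down in order to secure long-term safety data on the 200 strength.

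The AE listings do not expose a misbooked event: "These listing include information of dose group, not dose at AE". A reader would have to cross-check them against the deviation listing and the planned/actual treatment listing.

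**Working it through.** **1. Reproduce the SAP's examples.** Inputs are the planned, actual and dose-at-AE columns in SAP 11.6.1. Rule applied: if actual differs from planned in every interval, use actual; otherwise use planned, including the planned switch. Entries are the FF strength.

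| Weeks | Length | Ex 1 actual / SAP | Ex 2 actual / SAP | Ex 3 actual / SAP |
|---|---|---|---|---|
| 0–4 | 4 | 100 / 100 | 100 / 100 | 100 / 100 |
| 4–12 | 8 | 100 / 100 | **200 / 100** | 100 / 100 |
| 12–24 | 12 | 100 / 100 | 100 / 100 | 100 / 100 |
| 24–36 | 12 | 100 / 100 | 200 / 200 | 100 / 100 |
| 36–52 | 16 | **200 / 100** | **100 / 200** | 100 / 100 |

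The rule reproduces all three SAP columns. The examples are therefore what the SAP intends, not a slip.

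**2. Compare with dose received.**

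- Example 1: 16 of 52 weeks misassigned (16/52 = 30.8%). The SAP books 52 weeks to 100 and 0 to 200; by dose received it is 36 and 16.
- Example 2: 8 + 16 = 24 of 52 weeks misassigned (46.2%). The SAP books 24 weeks to 100 and 28 to 200; by dose received it is 32 and 20. The two errors partly offset in the totals, but AEs in both intervals still fall in the wrong table.
- Example 3: 0 weeks misassigned.

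**3. Study level.** The number affected, k, is not in the documents and is assumed here. With 110 participants (Protocol 10.1), 110 × 52 = 5,720 participant-weeks. The share misassigned is k × 16 to k × 24 over 5,720.

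| k (assumed) | Share misassigned |
|---|---|
| 0 | 0% |
| 1 | 0.3–0.4% |
| 5 | 1.4–2.1% |
| 11 | 3.1–4.6% |

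The 16 to 24 weeks are borrowed from the SAP's illustrations. One wrong 30-dose inhaler at one dose a day is 30/7 = 4.3 weeks, and 4.3/5,720 = 0.075%.

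**4. Row level.** SAP 2.3 sets no allocation ratio, so the table size n is also assumed. One participant moves an incidence by 100/n points. The cut-off for most common AEs is 3% (SAP 8.2), which is reached at ceil(0.03n) participants.

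| n (assumed) | Shift from one participant | Participants needed for 3% |
|---|---|---|
| 20 | 5.0 points | 1 |
| 55 | 1.8 points | 2 |
| 90 | 1.1 points | 3 |

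The shift occurs only if an AE starts in the wrong-strength interval and that participant is not already counted for the same term in that table.

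**The case against.** The strongest case concerns weight.

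- **Purpose.** Protocol 5.4 says the main aim is the safety of FF/UMEC/VI overall at UMEC 62.5 mcg, with no group comparison and no tests. The integrated summary is untouched.
- **Rarity.** Supply runs through the IRT, and dose and identity are checked at site dosing, so strength errors may never occur. The larger values of k have no source, and 16 wrong weeks would need every inhaler in that interval to be wrong.
- **Disclosure.** The rule is written down and illustrated, and incorrect treatment is an important protocol deviation that is summarised and listed.
- **Reading.** Under planned conduct the two approaches differ only for Week 24 switchers, so the protocol phrase might be aimed at them, and the SAP does handle them by dose taken.
- **Remedy.** Declaring the rule in SAP 2.1 and adding a sensitivity table would close the gap with less work.

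The points on size stand: the effect is unknown, probably small and possibly nil, and the integrated results do not change. The switchers-only reading does not stand, because the SAP itself uses received dose for whole-period errors. Disclosure elsewhere in the SAP does not make the statement in SAP 2.1 correct. The lighter remedy would cure the undeclared change, but the main tables would still not be the ones the protocol describes.

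**Conclusion.** The concern holds and should be fixed. For part-period strength errors, the final dose-at-AE tables depart from Protocol 10.3.2 and from the as-treated ITT definition, and SAP 2.1 says otherwise. The contradiction rests on the text alone. Its numerical effect depends on how many participants receive a wrong strength and for how long, which the documents do not give: from nothing to 4.6% of participant-weeks under the assumptions shown, and up to 5.0 points on a single row of a small table.

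The finding is confined to those participants and those tables. It concerns how AEs are classified and implies no view on dosing.

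**What to change.** In SAP 5.1.2.2, 8.2, 11.3.2.3 and 11.6.1:

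1. Define dose at AE as the strength actually received in the dispensing interval containing the AE onset date, taken from the planned/actual treatment records behind Listing 47.
2. Reclassify only when the strength differed. Under SAP 4.1 a negative answer to the eCRF question on correct treatment means "this participants will be regarded as having received an incorrect container", which need not be a different strength.
3. State a rule for intervals that mix strengths. Weeks 36–52 need 16 × 7 = 112 doses, and 112/30 = 3.7, so at least four inhalers; dates of use per inhaler are not described. One option is to footnote such AEs as strength uncertain.
4. Use as denominators the participants exposed to each strength.
5. Correct Examples 1 and 2.
6. If an allocated-dose version is kept, label it supplementary and declare it in SAP 2.1.

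Separately, SAP 5.1.1 uses allocated dose for the whole interim analysis. That should be reconciled with the as-treated ITT definition, using treatment received up to Week 24.

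The cost is SAP wording, a derivation with its mixed-interval rule, and a denominator rule. Before programming, confirm that the Listing 47 data hold strength at the level needed, since its shell is noted as still in development. The drawback is that an affected participant can count in both dose tables, even after brief exposure to one strength, which slightly dilutes incidence there. If no strength error occurs, the tables do not change.
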